6.4 Dose Selection and Justification

Based on the pharmacodynamic data and the dose/tumor size correlation observed (refer to IB, Section 4.2.1.4), 0.2 mg RGT100 can be considered a pharmacologically active dose for intratumoral injection when extrapolated from tumors in mice to a human lesion with a diameter of 20 mm.

Accordingly, a starting dose (DL1) of 1 mL (0.2 mg) of RGT100-PEI is being considered for the first-in-human clinical study of intratumoral/intralesional injection into cutaneous or hepatic lesions. Results from the 4-week toxicity studies in mice and cynomolgus monkeys suggest the following NOAELs and human equivalent doses (HEDs) after IV administration of RGT100-PEI:

- NOAEL/maximum tolerated dose (MTD) in mice = 1.6 mg/kg IV → HED = 0.13 mg/kg
- NOAEL in cynomolgus monkeys = 0.16 mg/kg → HED = 0.05 mg/kg
- MTD in cynomolgus monkeys = 1.5 mg/kg → HED = 0.5 mg/kg

Leakage of RGT100-PEI from the lesion after intratumoral injection is expected to be marginal because, after intratumoral injection in mice, 100% of the compound remained local

(refer to IB, Section 4.2.1.4). However, for the calculation of safety margins, complete leakage (eg, accidental administration into a blood vessel) was used as a worst case assumption. A theoretical complete leakage from a cutaneous lesion was mimicked in the SC toxicity studies. Local toxicity after direct injection into the liver was not examined, but results from a preliminary biodistribution study showed that most RGT100 is found in the liver after IV injection. Therefore, the IV toxicity data can be used to extrapolate the safety of leakage into healthy liver tissue.

Thus, assuming a theoretical complete systemic ad hoc exposure after intratumoral administration, a starting dose of 1 mL (0.2 mg RGT100) in a 60 kg human (0.0033 mg/kg) would lead to the following safety factors (calculated with unrounded raw data):

- Safety factor for mouse NOAEL/MTD: $0.13/0.0033 = 40$
- Safety factor for cynomolgus monkey NOAEL: $0.05/0.0033 = 15$
- Safety factor for cynomolgus monkey MTD: $0.5/0.0033 = 150$

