8.1.1 Dose Escalation Phase

This phase of the study will investigate increasing DLs of RGT100-PEI to determine the MTD or maximum feasible dose (MFD). The MFD is the highest dose volume that is safe and tolerable, and is feasible for intralesional/intratumoral injection. The MFD may be lower

than the MTD. The MTD (or MFD if lower than MTD) will define the RP2D to be used in the expansion phase of the study.

RGT100-PEI will be at a fixed concentration of 0.2 mg/mL and dose escalation will be based on the total volume of RGT100-PEI injected per subject. The planned DLs to be investigated in this phase of the study are:

- DL1: 0.2 mg = 1 mL
- DL2: 0.4 mg = 2 mL
- DL3: 0.6 mg = 3 mL
- DL4: 0.8 mg = 4 mL*

*Dose escalation may continue if deemed appropriate by the Safety Review Committee (SRC) (refer to [Section 10.5](#) for SRC details). The corresponding next dose levels beyond the above and the supporting safety data to continue will be described within a substantial amendment to this protocol which will only be implemented once approval has been received.

It is not expected that a MTD will be reached at the proposed dose levels. It is more likely that a maximum feasible dose will be reached before the MTD, defined as the maximum volume which can be injected into a lesion. Experience with other compounds which are also injected intratumorally/intralesionally was taken into consideration when planning the proposed dose levels and the initially proposed highest dose. However according to the nature of a phase I trial the maximum tolerable and/or feasible dose level are yet unknown and cannot be predicted.

The specific properties of RGT100-PEI being an immune-modulating drug is taken into consideration and safety will be closely monitored to detect any early signs of toxicity in general and dose limiting toxicities in particular.

For each DL the second and subsequent subject treated will start treatment at least 7 days following the first subject's injection to allow initial assessment of safety data by the treating Investigator and to report any serious potential safety concerns such as DLTs.

Group A will commence dosing first. Group B will commence dosing once DL2 has been shown to be safe and well tolerated in Group A subjects. Dosing will then commence at DL2 for Group B.

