8.4.1.1 Injection of RGT100-PEI – Tumor Selection

Injections should be targeted at viable tumor tissue and not at necrotic tissue. The Investigator may use his or her judgement to determine which tumors are accessible and injectable, and select an index lesion for injection. The accessibility and injectability will be assessed in accordance with routine medical practice (e.g., by physical palpation [SC lesions], by ultrasound or computerized tomography [CT] guidance if necessary [liver lesions]; in Germany only ultrasound guidance may be used). There will be documentation of the method

of assessment and various characteristics of the selected lesion (presence or absence of necrosis, ulceration, progression and prior local therapies).

It is up to the Investigator's discretion to select the index lesion and the lesion that serves as reference lesion.

There should be at least 1 measurable lesion left untreated, to meet the secondary endpoint of assessing changes in untreated disease and for irRECIST-assessment.

There is no limit to the proximity of the lesions selected for injection, except:

- Injected lesion(s) must be clearly distinguishable
- The un-injected lesion selected for observation (reference lesion) must be sufficiently remote from an injected lesion to allow for evaluation over a 60/90 day duration of the study.

The Investigator should make all efforts to apply the whole volume of drug into the chosen index lesion especially during the escalation phase.

The total volume of drug should be injected into the chosen index lesion. All lesions will be injected either directly or under image guided control (e.g., ultrasound). At each injection, the operator should collect the following information:

- Location of the lesion in the body
- Size of the injected lesion
- NCI CTCAE grading inflammation at the site and time of injection, if any, before and after injection
- Type of lesion injected (skin, lymph node, liver)
- Planned volume to be injected in the lesion (for eventual intent-to-treat analysis)
- Actual volume injected in the lesion (for eventual per dose received analysis)

The total volume of the corresponding dose level should be injected into the chosen index lesion. Only in cases where this is not possible the investigator will be allowed to split the total volume of a DL and inject the remaining volume into another lesion. The total volume of the applicable DL must not be exceeded.

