In the instance that a lesion exhibits complete response (CR) during the 4 weeks of therapy, the Investigator will be allowed to choose additional lesions for injection. The Investigator always needs to document which lesion(s) has/have been injected.

In order to avoid a non-injected target lesion becoming an injected lesion (and therefore rendering a subject as non-interpretable), it will be required that during the screening period the radiologist and the interventional radiologist (or Investigator) define together the non-injected lesions to be followed by irRECIST and list by priority order the lesion to be injected during the treatment.

Depending on the specific dose level and thus the amount of volume to be injected, the investigator should choose the index lesion for injection accordingly based on its size. The following algorithm below should be used as a guidance. However, it is up to the investigator to select an appropriate index lesion considered feasible for the volume to be injected, which may also be a bigger or smaller lesion.

- Dose level 1: 1.0 mL for lesions of 1.0 to 2.0 cm longest diameter
- Dose level 2: 2.0 mL for lesions of > 2.0 to 3.0 cm longest diameter
- Dose level 3: 3.0 mL for lesions of >3.0 to 5.0 cm longest diameter
- Dose level 4: 4.0 mL or more for lesions > 5 to 7 cm longest diameter

The measurement will be of the longest diameter of vital tumor tissue. In the event that it is not possible to assess the discrete size of the vital tissue, the maximum volume injectable should be pro-rated according to the percentage composition of necrotic tissue. The Investigator should also consider the tumor type and the tumor density in determining the lesion to be injected at the corresponding dose level.

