8.4.1.2 Injection of RGT100-PEI – Preparation

RGT100-PEI dispersion is available in 10-mL ready-to-use vials with an extractable volume of 5 mL containing 0.2 mg/mL. The vials should be stored frozen at -20°C (±5°C).

The following steps should be taken before injection:

- Thaw RGT100-PEI vial(s) to room temperature. It is recommended to administer RGT100-PEI within 4 hours.
- Draw the desired amount of RGT100-PEI from the vial into a syringe directly before the injection. Note: the vials of RGT100-PEI are for single use only and any unused dispersion has to be discarded.
- Clean the lesion and/or surrounding areas with an alcohol swab or other appropriate agent and let dry.
- For intrahepatic lesions follow routine procedure for preparation of the injection site.
- Cutaneous and subcutaneous lesions: Anesthetic agents should be avoided if possible as there is no knowledge if there may be an interaction between RGT100-PEI and an anesthetic agent. In case of severe pain, the injection site may be treated with a topical anesthetic agent.

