8.4.6 Selection of Doses in the Study

The concentration of the RGT100-PEI particles in the injection dispersion is fixed to 0.2 mg/mL to achieve stable complexes. Volumes of RGT100-PEI will be escalated to provide total doses of, for example, 0.2, 0.4, 0.6, and 0.8 mg per injection.

The planned starting dose of 1 mL (0.2 mg) for the dose escalation phase of the study is based on pre-clinical data (refer to [Section 6.4](#) for dose justification). To date there are no human data for RGT100-PEI.

Subsequent dose escalation will be based on the safety findings of the previous dose following review by the SRC (refer to [Section 8.1.1](#) for dose escalation details).

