8.4.9.4 Dose Modification and Dose Delay

Every effort should be made to administer trial treatment on the planned schedule. If a dose is missed, the dose should be administered as soon as possible. There should be at least 2 days between consecutive injections.

Treatments visits can be moved by 1 day when necessary for logistical purposes.

The End-of-Treatment Visit (Day 29) can be moved by ± 3 days and follow-up visits can be moved by ± 7 days when necessary.

The toxicity of treatment must be recorded before the administration of the next dose and graded according to the current version of the NCI CTCAE version 4.03. If individual

subjects experience treatment-related toxicity, subsequent trial treatment may be delayed as described below. Dose reductions are not permitted.

For grade 3, grade 4, or intolerable grade 2 toxicities, the treatment will be interrupted until recovery to \leq grade 1 or to baseline. Trial treatment will be permanently discontinued if the subject fails to recover to this extent within 3 weeks. Dose reductions or modifications are not allowed in both, the dose escalation and expansion phase.

If a subject cannot tolerate treatment despite the dose delays, trial treatment will be discontinued. The subjects will then undergo end of treatment visit and will be followed up according to plan.

In the event of a RGT100-PEI overdose (defined as any dose above the applicable DL), the Investigator should report such an overdose via the SAE form immediately and closely monitor the subject for AEs. The Investigator will use clinical judgement to treat any overdose.

Treatment is to be discontinued prematurely in the following situations:

- Complete response
- All injectable lesions have disappeared
- Intolerance of study treatment
- Subject withdrawal

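### The lesion-size guidance gives dose level 4 an open-ended volume, against its fixed 4 mL definition, the volume cap, the overdose rule and the amendment requirement

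*Combined protocol and SAP*

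**What the plan says.** Section 8.4.1.1 offers guidance for matching the index lesion to the volume to be injected. Levels 1, 2 and 3 are paired with exactly 1.0, 2.0 and 3.0 mL. The fourth line differs: "Dose level 4: 4.0 mL or more for lesions > 5 to 7 cm longest diameter".

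Four other provisions bear on that line:

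- **Definition.** The Synopsis, Section 8.1.1 and Table 2 in Section 8.4.9.1 all set level 4 at 0.8 mg in 4 mL. The concentration is fixed at 0.2 mg/mL, so volume alone sets the dose.
- **Cap.** Shortly before the guidance list, Section 8.4.1.1 states: "The total volume of the applicable DL must not be exceeded".
- **Overdose.** Section 8.4.9.4 describes an "RGT100-PEI overdose (defined as any dose above the applicable DL") and adds that "the Investigator should report such an overdose via the SAE form immediately".
- **Higher levels.** Under the Synopsis and Section 8.1.1, levels beyond the fourth, with their supporting safety data, "will be described within a substantial amendment to this protocol which will only be implemented once approval has been received".

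Section 8.4.1.1 also requires the planned and the actual volume to be recorded at each injection. Section 11.1.3.2 then summarises percentage intended dose, the delivered dose relative to the intended dose through progression.

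**The concern.** Dose level 4 has one volume in three places and a lower bound without an upper bound in a fourth. The fourth place is the list that an operator would consult when pairing a lesion with a volume.

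The guidance does leave the investigator some freedom, since the index lesion may be larger or smaller than the band suggests. That freedom concerns which lesion to choose. It does not say that the volume of the assigned level may vary.

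Two things are at stake in a first-in-human trial. The first is classification: one site could regard an injection above 4 mL as following the guidance, and another could report it as an overdose. The second is the exposure data: the planned volume entered for that injection, and any percentage intended dose built on it, would depend on which section the site had in mind.

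**Working it through.** **Inputs.** Concentration 0.2 mg/mL (Section 8.1.1). Volumes of 1, 2, 3 and 4 mL and doses of 0.2, 0.4, 0.6 and 0.8 mg (Section 8.4.9.1, Table 2). Injections per first cycle: 8 in Group A and 4 in Group B (Tables 3 and 4).

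**Step 1: reproduce the plan's doses.** Dose = concentration × volume.

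| Level | Calculation | Result | Stated |
|---|---|---|---|
| 1 | 0.2 × 1 | 0.2 mg | 0.2 mg |
| 2 | 0.2 × 2 | 0.4 mg | 0.4 mg |
| 3 | 0.2 × 3 | 0.6 mg | 0.6 mg |
| 4 | 0.2 × 4 | 0.8 mg | 0.8 mg |

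All four agree, so the declared level 4 dose corresponds to 4 mL and to no other volume.

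**Step 2: volumes that the open-ended line admits.** The documents propose no volume above 4 mL, so these are illustrations.

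- 4.5 mL: 0.2 × 4.5 = 0.9 mg; 0.9/0.8 = 1.125, or 12.5% above level 4.
- 5 mL: 0.2 × 5 = 1.0 mg; 1.0/0.8 = 1.25, or 25% above level 4.

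The second is physically possible from one vial, which is supplied "with an extractable volume of 5 mL containing 0.2 mg/mL".

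**Step 3: how each provision would read one 5 mL injection at level 4.**

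| Provision | Reading |
|---|---|
| 8.4.1.1, guidance line for level 4 | Within the stated range |
| Synopsis, 8.1.1, 8.4.9.1 | Not the level 4 dose |
| 8.4.1.1, cap | Not permitted |
| 8.4.9.4 | Overdose, SAE form |
| Synopsis, 8.1.1, further levels | A higher level would first need an approved amendment |

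**Step 4: effect on percentage intended dose.** Section 11.1.3.2 does not say whether the intended dose comes from Table 2 or from the recorded planned volume. Assume a complete first cycle at 4 mL except for one 5 mL injection:

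- Group A: intended by Table 2, 8 × 4 = 32 mL; delivered, 7 × 4 + 5 = 33 mL; 33/32 = 103%.
- Group B: intended, 4 × 4 = 16 mL; delivered, 3 × 4 + 5 = 17 mL; 17/16 = 106%.

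If the 5 mL had been entered as the planned volume on the strength of the guidance line, the same subjects would show 33/33 and 17/17, that is 100%.

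**The case against.** The strongest defence is that the rest of the protocol leaves little doubt. The list is introduced as guidance for choosing a lesion once the volume is known. Section 8.4.1.3 ties the total volume to the current dose level, Section 8.4.5 has the dose confirmed by email when the medical monitor approves enrolment, and Section 8.4.9.4 rules out dose modifications. There are also innocent readings. The line may describe what a large lesion can hold, since the text after it speaks of pro-rating the maximum injectable volume for necrosis. Or it may point to later levels, since the note on continued escalation is attached to level 4.

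This stands as mitigation. It makes misuse less likely, but the line is labelled as dose level 4 and states neither of those meanings.

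The defence is also right about several stronger inferences that a reader might draw:

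- **Percentage intended dose would read 125%.** That needs every injection to be 5 mL (40/32 or 20/16). One such injection gives 103% or 106% over a first cycle.
- **Vial size shows an intended 5 mL dose.** Vials are single-use and the remainder is discarded, so the fill volume says nothing about the planned dose.
- **The animal safety margins are eroded.** Section 6.4 computes them for "a starting dose of 1 mL (0.2 mg RGT100) in a 60 kg human (0.0033 mg/kg") under complete leakage, as a worst case. Scaling them linearly to 4 mL describes the declared level 4, not the open-ended wording. Going further needs an assumed volume that the documents do not propose.
- **Section 8.4.6 also leaves the dose open.** Its wording, "total doses of, for example, 0.2, 0.4, 0.6, and 0.8 mg per injection", lists exactly the four planned doses, and the section refers the reader to Section 8.1.1, where the amendment rule stands.
- **The level 4 cohort will mix doses, or the maximum feasible dose will come from an undeclared volume.** Either would require sites to disregard the cap, Table 2 and the dose confirmation, and dose decisions go through the Safety Review Committee. This is possible, but the documents give no reason to expect it.
- **Lesion size confounds dose level and the analysis omits it.** The size bands do not bind. From level 1 to level 4 at band mid-points (1.5 and 6 cm), dose per unit lesion volume falls 16-fold for spheres and 4-fold for flat lesions of equal thickness, while dose per cm of diameter does not change. Lesion size and volumes are recorded, Section 12.5 plans listings of all clinical data, and the separate analysis plan announced in Section 11.1.5 is not among the documents. A further display would be optional.

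**Conclusion.** The level 4 line in Section 8.4.1.1 is wrong as written and should be corrected. It conflicts with the fixed 4 mL definition given in three places, the volume cap in its own section, the overdose definition in Section 8.4.9.4, and the requirement for an approved amendment before going beyond level 4. This conclusion is a comparison of current texts and needs no statistical assumption.

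Its size is bounded. Any volume above 4 mL exceeds 0.8 mg, and the illustrative 5 mL injection exceeds it by 25% for that injection. The practical consequence is an injection that can be classed in two ways, with planned volume and percentage intended dose following whichever class was chosen. The cycle-level figures of 103% and 106% rest on one 5 mL injection in an otherwise complete first cycle at 4 mL. The documents do not show that such injections are intended or likely.

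**What to change.** Reconcile the level 4 line in Section 8.4.1.1 with the Synopsis, Section 8.1.1, the cap in Section 8.4.1.1, Table 2 in Section 8.4.9.1 and the overdose definition in Section 8.4.9.4. One volume definition should then govern the planned volume recorded at each injection, the classification of an overdose, and the intended dose used in Section 11.1.3.2. If the line was meant to describe lesion capacity or to anticipate amended levels, it needs to say so. This review takes no view on which text is right and proposes no volume; that is for the sponsor.

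The cost is protocol wording only. No new data, visits or analyses are needed.

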8.3.2 Inclusion Criteria

A subject will be eligible for inclusion in this study if all of the following criteria apply:

1. Male or female aged ≥ 18 years

2. Subjects with histologically or cytologically confirmed diagnosis of advanced or recurrent tumors (including lymphomas) for whom all standard treatments have been used or are not feasible or RGT100-PEI is a suitable treatment option and:
 - a. For Group A: has cutaneous, SC, or lymph node injectable tumors
 - b. For Group B: has injectable liver tumors or liver metastases
3. Eastern Cooperative Oncology Group (ECOG) performance status 0-2
4. Life expectancy > 3 months as assessed by the Investigator
5. Adequate organ function:
 - a. Bone marrow function: Hemoglobin ≥ 10 g/dL (pre-treatment transfusion allowed); lymphocyte count $\geq 0.5 \times 10^9/L$; absolute neutrophil count $\geq 0.5 \times 10^9/L$; platelet count $\geq 75 \times 10^9/L$
 - b. Hepatic function: AST and ALT $\leq 2 \times$ upper limit of normal (ULN) ($3 \times$ ULN in the case of liver metastases); bilirubin $\leq 1.5 \times$ ULN ($2 \times$ ULN in case of liver metastases)
 - c. Renal function: creatinine $< 1.5 \times$ ULN and/or creatinine clearance ≥ 50 mL/min (Cockcroft and Gault)
6. Negative serum pregnancy test within 2 weeks before first dose of study drug if the subject is a woman of childbearing potential. Subjects and subjects' partners of childbearing potential must agree to use birth control consistently and correctly during the study and for at least 6 months after the last study drug application.
7. At least 1 measurable lesion per RECIST 1.1 and 1 separate injectable lesion with diameter ≥ 1 cm but < 7 cm
8. Ability to provide written informed consent before any study drug-related screening procedures being performed

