- Dispose of all materials that have come in contact with RGT100-PEI (e.g., vial, syringe, needle, any cotton or gauze) in accordance with local institutional procedures.

The Investigator should note and record any unusual backpressure to the injection, any suspicion of leakage of injected material beyond the index lesion and any reasons why the predicted volume to be injected into an individual lesion was not achievable.

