11.1.2 Datasets or Populations Analyzed

All subjects enrolled in the study will be accounted for. The number of subjects who were NE, who died, or who withdrew before treatment began will be recorded. All subjects who received at least 1 dose of the study drug will be included in the analysis for toxicity.

Two subject populations will be used for the analyses:

- The safety population will consist of all enrolled subjects who received at least 1 dose of RGT100-PEI.
- The evaluable population will consist of all enrolled subjects who complete Week 4 or withdraw early for experiencing a DLT.

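### DLT evaluability has no received-dose criterion, so a dose level can be cleared partly on subjects who were given less than its volume

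*Combined protocol and SAP*

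**What the plan says.** Section 8.1.1 fixes the concentration at 0.2 mg/mL and escalates on total volume per subject: 1, 2, 3 and 4 mL for DL1 to DL4. Section 8.4.1.1 states the aim, "The total volume of the corresponding dose level should be injected into the chosen index lesion", and adds that, failing this, "the investigator will be allowed to split the total volume of a DL and inject the remaining volume into another lesion". Its guidance on matching lesion size to dose level ends with a rule for lesions whose viable part cannot be measured: "the maximum volume injectable should be pro-rated according to the percentage composition of necrotic tissue". Section 8.4.1.3 asks the operator to record "any reasons why the predicted volume to be injected into an individual lesion was not achievable". Section 8.4.1.4 expects that a lesion which has shrunk may no longer hold the planned volume. Inclusion criterion 7 (Section 8.3.2) asks for "At least 1 measurable lesion per RECIST 1.1 and 1 separate injectable lesion", and Section 8.4.1.1 wants at least one measurable lesion left untreated.

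For the analysis, Section 11.1.2 reads: "The evaluable population will consist of all enrolled subjects who complete Week 4 or withdraw early for experiencing a DLT". Section 11.1.2.1 uses the same set for dose escalation and reports DLTs by dose level. Section 8.3.4.2 adds that subjects who miss more than 2 injections (Group A) or more than 1 (Group B) because of drug-related toxicity short of a DLT are replaced for DLT evaluation. Section 8.4.9.4 says: "Dose reductions or modifications are not allowed in both, the dose escalation and expansion phase".

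**The concern.** The 3+3 rule in Table 1 reads each DLT-free subject as evidence that the level's volume is tolerated. That holds only if the volume was given. The plan foresees cases where it is not, and it records the actual volume and the reason for any shortfall, but neither affects whether the subject counts.

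The recommended Phase 2 dose is a primary objective. Section 8.1.1 expects the maximum feasible dose (MFD), rather than the maximum tolerated dose, to set it. A level whose volume was often not delivered could then look both tolerated and feasible.

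**Working it through.** **The plan's own figure.** Section 11.2.1 gives 9 to 24 evaluable subjects per group. Four levels of up to 6 give 4 × 6 = 24 (Group A). Three levels of at least 3 give 3 × 3 = 9 (Group B, which starts at DL2). The range reproduces as a count of levels and carries no DLT rate. Cohorts are 3 or 6, so each evaluable place weighs heavily.

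**Two definitions of evaluable, side by side.**

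- A Group A subject who misses 3 of 8 injections for drug-related toxicity is replaced under Section 8.3.4.2. If that subject completes Week 4, Section 11.1.2 still counts the subject as evaluable.
- A Group A subject at DL4 who receives half the volume at all 8 visits misses no injection, so the missed-injection rule does not apply. The total is 8 × 2 = 16 mL of a planned 8 × 4 = 32 mL, or 50%. Both sections leave this subject counted at DL4.

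**What a shortfall means in dose.** The necrotic share is an assumption, and the remainder is taken as not given elsewhere. At 25%, DL4 becomes 4 × 0.75 = 3 mL, or 0.6 mg, the DL3 dose. At 50% it becomes 4 × 0.5 = 2 mL, or 0.4 mg, the DL2 dose.

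**Effect on Table 1.** A level is cleared with 0 DLTs in 3 subjects, or with 1 in 3 followed by 0 in the next 3. Let m of every 3 subjects be under-dosed with DLT risk q, and let the others have risk p. Let A be the chance of no DLT in three subjects and B the chance of exactly one. Then P(clear) = A + B × A, where A = (1 − q)^m × (1 − p)^(3 − m).

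- p = 0.40, m = 0: A = 0.216, B = 0.432, P = 0.216 + 0.432 × 0.216 = 0.309.
- p = 0.40, q = 0.20, m = 1: A = 0.8 × 0.36 = 0.288, B = 0.072 + 0.384 = 0.456, P = 0.288 + 0.456 × 0.288 = 0.419.
- p = 0.40, q = 0.10, m = 1: A = 0.9 × 0.36 = 0.324, B = 0.036 + 0.432 = 0.468, P = 0.324 + 0.468 × 0.324 = 0.476.
- p = 0.10, m = 0: A = 0.729, B = 0.243, P = 0.729 + 0.243 × 0.729 = 0.906.
- p = 0.10, q = 0.05, m = 1: A = 0.95 × 0.81 = 0.7695, B = 0.0405 + 0.171 = 0.2115, P = 0.7695 + 0.2115 × 0.7695 = 0.932.

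All risks are assumptions, because the documents give none. In every row but the third, q is half of p, as it would be if risk were proportional to dose and half the volume were given.

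| Risk at full volume | Risk at reduced volume | None under-dosed | 1 of every 3 | All |
|---|---|---|---|---|
| 50% | 25% | 17% | 27% | 60% |
| 40% | 20% | 31% | 42% | 71% |
| 40% | 10% | 31% | 48% | 91% |
| 33% | 16.5% | 43% | 54% | 78% |
| 10% | 5% | 91% | 93% | 97% |

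**The case against.** A reader might infer that Section 8.4.1.1 itself orders a lower dose. The text does not support that. It pro-rates the most a given lesion can take, only when viable tissue cannot be sized, and it does so within guidance on choosing a lesion that fits the level. The subject's total falls only if the remainder is not given elsewhere. The plan works against that: all efforts are to be made to give the whole volume, lesions for injection are ranked at screening, and other lesions may take the rest. This stands, and it limits how often a shortfall will occur. It does not remove the case of a subject with a single injectable lesion.

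A flat contradiction with the ban on dose modification in Section 8.4.9.4 is likewise more than the text shows. That ban sits among instructions on toxicity, although its wording is general enough to need reconciling.

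Section 11.1.3.2 already summarizes relative dose intensity and percentage of intended dose, so exposure is not ignored. It is not linked to DLTs, evaluability or the MFD. Section 11.1 defers detail to a separate analysis plan that is not part of the text reviewed.

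Section 8.3.4.2 also allows replacement for non-compliance. That is optional, and a lesion that cannot hold the volume is not obviously non-compliance.

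Finally, one might conclude that up to 60 expansion subjects would be treated on a false reading. The documents place Safety Review Committee (SRC) judgment, a safety report covering feasibility, a protocol amendment and acceptance by authorities in between (Sections 10.5 and 8.1.2). None of these is required to look at delivered volume, but the consequence is not automatic.

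**Conclusion.** The gap is real but narrower than the pro-rating sentence suggests. Following the plan as written, a DLT-free subject who received less than the dose-level volume counts in full, and the replacement rule and the evaluable population do not agree.

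The size depends on assumptions. With one of every three subjects under-dosed, the chance of clearing a level rises by about 3 percentage points (91% to 93%; 0.906 to 0.932 before rounding) when risks are low and by up to 17 (31% to 48%) when they are high and fall fourfold at the reduced volume. Section 8.1.1 does not expect a maximum tolerated dose at the planned levels, which makes the low-risk end plausible. The direction holds whenever DLT risk rises with dose. Nothing in the documents says how many subjects would be under-dosed, so the last column of the table is a bound, not a forecast.

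**What to change.** 1. Use one definition of DLT-evaluable in Sections 8.3.4.2, 11.1.2 and 11.1.2.1, with a pre-specified minimum percentage of the cycle's planned volume (planned injections × dose-level volume) actually injected. A DLT always counts. DLT-free subjects below the minimum are replaced and stay in the safety population. State how subjects who stop early for complete response are handled, since a blanket rule would exclude them. The sponsor sets and justifies the threshold. One option is 75%, extrapolated from the injections that may be missed under Section 8.3.4.2 (6 of 8 or 3 of 4 received); it is not an existing volume rule.
2. Extend the exposure summary in Section 11.1.3.2 to show, by group and dose level, the percentage of planned volume given into the index lesion and DLT status against actual volume. Supply it to the SRC and use it to support the MFD statement.
3. The sponsor must reconcile Sections 8.3.4.2, 8.4.1.1, 8.4.1.4, 8.4.9.4, 11.1.2 and 11.1.2.1. No dose or clinical rule is proposed here.

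The cost is wording, one table from data already collected, and an occasional replacement subject. If shortfalls proved common, cohorts would fill more slowly, and that would itself be information on feasibility.
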